8 ANALYSIS CONVENTIONS

8.1 General principles

Analysis structure

Separate analyses will be performed for Part 1 and Part 2.

The analysis for Part 1 will take into consideration the Treatment Period of Part 1. For Part 1, all presentations will be done per treatment arm, i.e., comparing the tapentadol arm to the morphine arm.

The analysis for Part 2 will take into consideration the Tapentadol Period and Observation Period of Part 2. Given that the different periods, i.e., Tapentadol Period and Observation Period, are not comparable, due to the heterogeneity of the populations (see Section 18.1.3 for additional information), all analyses of Part 2 will be illustrated separately for the Tapentadol and Observation Period as detailed below, if not specified differently.

For the Tapentadol Period, all statistical analyses will be presented by the following arms:

- Subjects in the Tapentadol Period pretreated with morphine during Part 1.
- Subjects in the Tapentadol Period pretreated with tapentadol during Part 1.
- All subjects in the Tapentadol Period.

For the Observation Period, all statistical analyses will be presented by the following arms:

- Subjects pretreated with morphine during Part 1 and continuing the trial in the Observation Period directly after Part 1.
- Subjects pretreated with tapentadol during Part 1 and continuing the trial in the Observation Period directly after Part 1.
- All subjects continuing the trial in the Observation Period directly after Part 1.
- Subjects discontinuing the Tapentadol Period before F12M and continuing the trial in the Observation Period.

Unless otherwise specified, descriptive summaries will be provided for each time point and for the change from baseline (defined in Section 8.2.2) to each time point. Additionally, for Part 2, the last assessment (defined in Section 8.2.2) and change from baseline to the last assessment will be summarized.

Data presented in subject data listings will be sorted by treatment if not specified differently.

Unscheduled measurements of laboratory parameters, vital signs and electrocardiogram will be presented in the subject data listing. In general, unscheduled measurements will not be included in the analysis. However, they will be considered in the derivation of the overall post-baseline value (see Section 18.1.12.1) that is used in the shift and alert frequency analyses.

Details on the programmatic derivation of the trial periods can be found in Section 18.1.2.10.

Summary statistics

Data collected in this trial will be summarized according to their nature as follows:

- Continuous variables: number of non-missing observations, arithmetic mean, standard deviation (SD), minimum and maximum values, median and quartiles. If there are less than 5 observations descriptive statistics will be presented based on the rules specified in Section 18.1.2.2.
- Categorical variables: absolute and relative frequencies. If not defined otherwise, the percentage denominator will be the number of subjects in the trial at the respective time point in the analyzed population.

- Time-to-event variables: Kaplan-Meier estimates together with the 95% confidence intervals (CI) will be provided with the respective number at risk and the number censored at the relevant time points. In addition, the median time-to-event and its 95% confidence interval for all arms will be presented. For calculating the survival estimate CI bounds, the log-log transformed estimate of CI bounds will be used. Censoring mechanisms depend on the specific endpoint and will be described in the respective section.

Details on rounding and presentation in case of missing data can be found in Section [18.1.2](#).

Coding of eCRF-entries

All Medication and additional therapies/treatments will be coded using the World Health Organization Drug Dictionary (WHO-DD) or in case of non-medicinal therapies via Medical Dictionary for Regulatory Activities (MedDRA). The versions of these reference documents will be specified on the appropriate statistical outputs.

All investigator-reported terms for medical history in the electronic case report form (eCRF) and all original terms used by the investigators in the eCRFs to identify adverse events (AEs) will be coded using the Medical Dictionary for Regulatory Activities (MedDRA).

For the final analyses, the latest version of the WHO-DD/MedDRA at the time of coding for final evaluations will be used. These might be different for the final analyses of Part 1 and the final analysis of Part 2. Coding for the DMC analyses is addressed in the DMC SAP.

8.2 Definitions

8.2.1 Definition of subgroup

For some parameters, statistical analyses will also be presented for the following subgroups:

- Age groups:
 - 6 years to less than 12 years.
 - 12 years to less than 18 years.

Age groups are determined using the age assessment at Visit V2 for both parts. In case of discrepancies between the IVRS/IWRS recording and the eCRF for age, the entry in the eCRF will be used for all analyses unless explicitly stated otherwise.

- Underlying pain condition (based on information from the eCRF at Visit V1)
 - Cancer related pain.
 - Non-cancer related pain.

Table 4: Subgroup analysis

	Age group	Underlying pain condition
Subject disposition	Enrolled Set	Enrolled Set
Demographics + other baseline characteristics (excluding medical history and prior and concomitant medication)	SAF	SAF
Descriptive statistics of primary efficacy endpoint	FAS	FAS
Exploratory statistical analysis and forest plots of primary efficacy endpoint as described in Section 13.1.3	FAS	FAS
Pain assessments	FAS	FAS
Acceptability and palatability questionnaire	FAS	-
Rescue medication	FAS	-
Serum concentrations of tapentadol and tapentadol-O-glucuronide	PK-Set	PK-Set
Incidence of TEAEs by SOC and PT (selected analyses)	SAF	SAF

8.2.2 Further definitions

Term	Part/Period	Definition
Pre-treatment-period	-	Before first IMP administration (excluded)
Therapeutic reach	-	
The therapeutic reach is the time after the last IMP intake that a subject is still considered to be potentially affected by a study drug.
 
For tapentadol PR and morphine PR, the therapeutic reach is defined as 72 hours after (last) IMP intake.

On-treatment-period	Part 1	
 • Subjects continuing in the Tapentadol Period after the Treatment Period: 
 a. Start: First IMP administration of Part 1 (included) b. End: 
 i. If the last administration of IMP during Part 1 is more than 3 days before Visit VE: Last administration of IMP during Part 1 + 72 hours (included, therapeutic reach) ii. If the last administration of IMP during Part 1 is less than 3 days before Visit VE: Visit VE (included) c. Start: First IMP administration (included) d. End: Last administration of IMP during Part 1 + 72 hours (included)
	Part 2	
Tapentadol Period only:
 
 a. Start: Visit VE (excluded in case VE is included in the on-treatment period of Part 1; included in case VE is not included in the on-treatment period of Part 1) b. End: Last administration of IMP during the Tapentadol Period + 72 hours (included)
Post-treatment-period	-	After last IMP administration drug intake + 72 hours (excluded)
Enrolled subjects	-	Informed consent form signed. If required by local law an assent form signed.
Treated subjects	-	Subjects with at least 1 administration of IMP.
Treatment completers	Part 1	
Subjects who have completed the 14-day Treatment Period.
 
Completion of the 14-day Treatment Period means that a subject performs the End of Treatment Visit (Visit VE) in the allowed window of 15 ± 1 days, i.e., at or later than Day 14, and has the last IMP intake of part 1 no earlier than Day 13 in the evening.

	Part 2	
Subjects who have completed the 12-month Tapentadol Period.
 
Completion of the 12-month Tapentadol Period means that a subject performs the 12-month follow-up visit (F12M) in the window of 365 ± 14 days, i.e., at or later than 351 days after Visit VE, as part of the Tapentadol Period.

Trial completers	Part 1	Subjects who have completed the 14-day Treatment Period and who performed Visit F7D or entered the Tapentadol Period of Part 2.
	Part 2	Subjects who fully completed the extension period, i.e., either subjects completing the Tapentadol Period and the follow-up visit (F12M and F7D) or subjects completing the Observation Period (F12M) not earlier than 351 days

Term	Part/Period	Definition
		after Visit VE.
Baseline values	Treatment Period	
 Baseline measurements are defined as the last evaluation performed before starting IMP (i.e., Visit V1, Visit V2 or unscheduled visit). For pain assessment, baseline pain is defined as “pain right now” at Visit V2, and will be assessed before any painful or unpleasant procedure, and before the first intake of IMP. Details on the programming aspects regarding the baseline pain intensity can be found in Section 18.1.5.3.
	Tapentadol Period:	Baseline measurements are defined as the last evaluation performed before or at Visit VE
	Observation Period:	
 Baseline measurements are defined as the last evaluation performed before or at Visit VE for subjects entering the Observation Period directly after Part 1 Visit ET for subjects switching from the Tapentadol Period to the Observation Period
Last assessment	Treatment Period	Assessment at Visit VE. Performed for all subjects completing Part 1 or discontinuing IMP early.
	Tapentadol Period	
 Assessment at Visit F12M for subjects completing the Tapentadol Period. Assessment at Visit ET for subjects discontinuing the Tapentadol Period prior to 12 months after Visit VE.
	Observation Period	
 Assessment at Visit F12M for subjects completing the Observation Period 12 month after Visit VE. Assessment at Visit OPx for subjects discontinuing the Observation Period prior to 12 month after Visit VE.

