- As time to discontinuation refers to discontinuation from *treatment*, it was specified that the dates of first and last IMP intakes should be used for the respective calculations rather than the dates of the scheduled visits.
- The protocol specifies that subjects should have taken their last IMP of the Treatment Period on the day of VE or the evening before. In reality; this intake might have occurred earlier, in particular for subjects that discontinued treatment. For the derivation of the primary endpoint, it was therefore specified that the last 3 days of treatment should be considered for pain assessment rather than the last 3 days prior to VE.
- The options of the multiple imputation were specified more clearly, covering how the imputation by treatment group should be done, which variables to be included in the model and how to handle the different pain scales and the ranges of their respective scores.
- The prior distribution for the precision of the random effects used in the Bayesian analysis of the primary endpoint was redefined based on the expert recommendation provided in the literature (Gelman 2016).
- The factor for the morphine PR equivalent of tapentadol PR that has to be used for some calculations was added.
- A specification of days to be considered for the SOWS (Day 0 = day of last IMP) was added, as deviating from trial day definition.
- For the Z-score related to *weight* and *height*, a rule to derive the age in months based on the available information in years was provided as required for the calculation.

7.2.2 Amendment 01

Amendment 01 to the final SAP was prepared to cover the following topics:

- Changes arising from protocol Amendment 02 dated 23 June 2015 and protocol Amendment 04 dated 23 May 2017 were implemented, including the following major changes:
 - The update of the alpha for the primary endpoint analysis based on the methodology proposed by Hlavin et al. (2016) with the consequence of sample size reduction and use of 80% confidence interval for the primary endpoint analysis.
 - The deletion of the interim analysis for the sample size reassessment due to the sample size reduction. The adaptive 2-stage design of the trial has been simplified to a fixed 1-stage design.

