- AEs starting on the day of Visit VE (including the last IMP intake of Part 1 and first IMP intake of Part 2 [eDiary and dispense information]).

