18.1.2.11 First and last IMP intake

The first and last IMP intake of the Treatment Period and of the Tapentadol Period will be specified based on the start and end dates provided on the IMP dispense form of the eCRF, supported by the eDiary data.

First IMP intake of the Treatment Period

The first IMP intake of the Treatment Period will be the date and time of the day (morning/evening) of the earliest start entry in the eCRF for the Treatment Period.

The time will be set to the time of the corresponding eDiary entry at that date and time of the day if available; else the time will be missing.

First IMP intake of the Tapentadol Period

The first IMP intake of the Tapentadol Period will be the date and time of the day of the earliest start entry in the eCRF for the Tapentadol Period.

The time will be set to the time of the corresponding eDiary entry at that date and time of the day if available; else the time will be missing.

Last IMP intake of the Treatment Period

The last IMP intake of the Treatment Period will be the date and time of the day of the latest end entry in the eCRF for the Treatment Period.

The time will be set to the time of the corresponding eDiary entry at that date and time of the day if available; else the time will be missing.

Last IMP intake of the Tapentadol Period

The last IMP intake of the Tapentadol Period will be the date and time of the day of the latest end entry in the eCRF for the Tapentadol Period.

The time will be set to the time of the corresponding eDiary entry at that date and time of the day if available; else the time will be missing.

In case the required information from the IMP Dispense form of the eCRF is not available, the first and last IMP intake assigned to the Treatment and Tapentadol Period in the eDiary will be used. In case the switch of the eDiary from the Treatment Period to the Tapentadol Period was missed, the date of Visit VE will be used for the last IMP intake of the Treatment Period and the first IMP intake of the Tapentadol Period, with time of the day and time missing.

18.1.3 Population heterogeneity during Part 2

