18.1.11.2 Assessments of pre-/on-/post-treatment-period

The calculation of the pre-/on-/post-treatment- period will be based on the date information given for IMP administration and for Visit VE (see Section [8.2.2](#)).

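### For practically all in-window subjects continuing into the Tapentadol Period, adverse events dated on Visit VE are tabulated in Part 1 even when they follow the first Tapentadol Period dose.

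*SAP*

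**What the plan says.** SAP 8.2.2 has two branches for the end of Part 1 on-treatment time in subjects who continue into the Tapentadol Period. The usual one reads "If the last administration of IMP during Part 1 is less than 3 days before Visit VE: Visit VE (included". The other applies "If the last administration of IMP during Part 1 is more than 3 days before Visit VE"; Part 1 then ends 72 hours after the last Part 1 dose.

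The Tapentadol Period window follows from this: "Start: Visit VE (excluded in case VE is included in the on-treatment period of Part 1". The first tapentadol dose is not a boundary in either definition. SAP 18.1.11.2 says that the periods "will be based on the date information given for IMP administration and for Visit VE", so VE counts as a whole calendar day. SAP 15.1.2 assigns a treatment-emergent event (TEAE) to the period in whose window it occurs, but refers to the start time of the event.

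On timing, SAP 7.2.1 reads the protocol as saying that "subjects should have taken their last IMP of the Treatment Period on the day of VE or the evening before". The protocol has Part 2 medication dispensed at VE.

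The SAP is aware of the overlap. SAP 15.1.2.2 plans a listing of "AEs starting on the day of Visit VE (including the last IMP intake of Part 1 and first IMP intake of Part 2", and SAP 15.1.2.1 has overview rows for Part 1 events still ongoing in the Tapentadol Period.

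**The concern.** A former morphine subject can take the first tapentadol dose on the VE date, have a new event some hours later, and appear in the tables with a Part 1 morphine TEAE and no Tapentadol Period TEAE.

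Tolerability by treatment group is a main secondary endpoint in both parts (Protocol 8.1.2, SAP 15.1). Two displays are affected. In Part 1, events that start after the drug has changed are shown under morphine. In the Tapentadol Period, the morphine-pretreated arm, which SAP 8.1 reports separately, loses events from the first hours after the switch. Protocol 11.1.2.1 gives that group two extra visits because withdrawal symptoms may occur when they change drug.

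**Working it through.** The plan gives no figure for this rule, so the check is mainly a reading of the definitions against each other, followed by the weight of one subject.

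**Inputs**
- N = 69 at 2:1 (SAP 5.2), so 46 tapentadol and 23 morphine. An exact calculation with the Farrington-Manning test gives 80.8% power at 46:23 (the asymptotic formula gives 78.4%). Nothing below depends on this.
- Completers: last Part 1 dose no earlier than the evening of Day 13, VE on Day 14 to 16 (SAP 8.2.2). Completion is required for entry to the Tapentadol Period (Protocol 1.3.3).
- Therapeutic reach: 72 hours for both drugs (SAP 8.2.2).
- Dosing interval about 12 hours (Protocol 10.2.2); tapentadol PR peaks at about 3 to 6 hours (Protocol 6.2).
- Incidence rate: subjects with the event divided by subjects in the arm; reporting cut-off 5% (SAP 15.1.2.2 and 15.1.2.3).

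**Step 1: which branch applies.** The longest in-window gap from last dose to VE is Day 16 − Day 13 = 3 calendar days, which is under 72 hours if VE takes place in the daytime. All other in-window gaps are shorter. The VE-inclusive branch therefore covers practically all in-window subjects. The other branch needs a late VE, for example Day 17 − Day 13 = 4 days. Counted in dates, a gap of exactly 3 days falls under neither branch.

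**Step 2: can the first tapentadol dose fall on the VE date?** If the last morphine dose is the evening before VE, a 12-hour interval puts the next dose on the VE date. If it is the morning of VE, the next dose is due that evening. Both fit the VE date, although no section states when the first Part 2 dose is taken.

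**Step 3: consistency with the rest of the plan.**
- From the day after VE, an event in a former morphine subject goes to the Tapentadol Period even within 72 hours of the last morphine dose. The post-dose hours of the VE date are the exception, and no reason is given.
- The EAIR clock starts at first intake (SAP 15.1.2.3), while VE-day events are outside the Tapentadol Period numerator.
- SAP 18.1.10 censors time to first rescue medication on the VE date at the time of the first Tapentadol Period intake where available. The boundary missing for adverse events is already used there.
- Protocol 14.2.7.1 makes a worsening in the Tapentadol Period a new TEAE for former morphine subjects. A worsening after the dose on the VE date falls in the Part 1 window, where SAP 18.1.11.4 merges consecutive episodes at the highest intensity.

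**Step 4: weight of one subject.** Let m and t be the numbers of morphine-arm and tapentadol-arm subjects who are counted in Part 1 only because of a post-dose VE-day event. The shift in the Part 1 difference (tapentadol minus morphine) is t/46 − m/23.

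| m | t | Shift |
|---|---|---|
| 1 | 0 | −1/23 = −4.3 points |
| 1 | 1 | 1/46 − 1/23 = −2.2 points |
| 1 | 2 | 2/46 − 1/23 = 0 |

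In the morphine-pretreated arm of the Tapentadol Period, one subject is 1/n. The documents give no entry rate, so n is an assumed range: 1/23 = 4.3%, 1/20 = 5.0%, 1/15 = 6.7%, 1/10 = 10.0%. With n of 20 or fewer, one omitted subject can decide whether a preferred term reaches 5%, provided no other displayed arm already does.

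**The case against.** The strongest reply is that this is a deliberate convention applied alike in both arms, in tables that are descriptive only (SAP 15 plans no between-arm safety tests). Tapentadol continuers also have their post-dose VE-day events counted in Part 1. This stands, and it defeats the inference a reader might draw that the rule can only favour tapentadol. Step 4 shows that only the difference between arms matters.

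Attribution is also uncertain. On the VE date a switcher is usually within about a day of the last morphine dose, well inside the 72-hour reach, so some post-dose events may be residual morphine effects. From the day after VE such effects go to tapentadol, so misattribution runs both ways. This stands as a limit on any causal reading. It does not explain why the post-dose hours of one date follow a different rule from every later hour.

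Not all early post-dose events are caught. With an evening first dose, assumed at 19:00 to 21:00, the 3 to 6 hour peak runs from 22:00 to 03:00, so many events would be dated the next day and counted in the Tapentadol Period.

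Nor do the events vanish. Ongoing ones appear in an overview row, and all VE-day events are listed with both intakes. But the listing changes no incidence, and the ongoing row misses events that resolve the same day.

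A reader might also attach a large figure. Assuming 12 to 18 switchers and a 10% to 20% event rate that day gives 12 × 0.10 = 1.2 to 18 × 0.20 = 3.6 subjects, or 5.2 to 15.7 points of 23. Neither rate is in the documents. Incidence counts a subject once, so a switcher who already had the event in Part 1 changes nothing, and the tapentadol arm would have its own shift.

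**Conclusion.** The rule does what the concern says, within limits. For practically all in-window subjects entering the Tapentadol Period, an event starting on the VE date belongs to Part 1 even if it follows the first Tapentadol Period dose. For former morphine subjects this places post-switch events under morphine and omits them from the Tapentadol Period TEAE and EAIR numerators.

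It would go too far to say that every VE-day event is so assigned, because a gap of more than 3 days puts VE in Part 2 and a gap of exactly 3 days is undefined. The documents also do not establish a bias in one direction or its net size. The firm figures are 4.3 points per newly counted subject in a 23-subject morphine arm, and the 5% cut-off turning on one subject if 20 or fewer switch.

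This rests on the date-level reading in SAP 18.1.11.2, on the first tapentadol dose being taken on the VE date, and on planned arm sizes. SAP 15.1.2 speaks of start time, but the first Tapentadol Period intake is not a boundary under that wording either. No confirmatory conclusion is affected. A main secondary safety endpoint is, and the correction is cheap.

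**What to change.** In SAP 8.2.2 and 18.1.11.2, for all subjects entering the Tapentadol Period from either arm, end Part 1 on-treatment time and start Part 2 on-treatment time at the date and time of the first Tapentadol Period intake. SAP 18.1.2.11 already derives it ("The first IMP intake of the Tapentadol Period will be the date and time of the day of the earliest start entry"), and SAP 18.1.10 already uses it for rescue censoring. Assign VE-day events by event start time, which the CRF collects (Protocol 12.6.1).

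If either time is missing, keep the present Part 1 default and show the affected events both ways. State which branch takes a gap of exactly 3 days. Keep the VE-day listing.

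The cost is SAP wording and a few lines of programming, with no new data. There are two small downsides. Intake time is missing when no matching eDiary entry exists, or when the date of VE has to stand in for both intakes, so those cases stay on the default. Some residual morphine effects on the VE date would also move to the Tapentadol Period, as already happens from the following day.

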10.3 Method of assigning subjects to treatment (allocation)

An interactive response technology system (voice and web based) will be used to assign a subject number at the Enrollment Visit (Visit V1) of Part 1 and to support the drug supply chain management processes of distribution and return. Details of the vendor and the system will be defined in a separate document and filed in the trial master file at the end of trial.

The investigator or person assigned by the investigator must log into the system using their own user identification number and a password. The investigator or person assigned by the investigator will enter the subject's number and other information required by the system to obtain a medication number. The medication number is then used to select the correct package of IMP to give to the subject.

10.3.1 Part 1

Subjects who comply with all inclusion criteria and do not meet any of the exclusion criteria will be randomly assigned to 1 of the 2 treatment arms at Visit V2 (Allocation Visit) for the duration of the Treatment Period.

Subjects will be stratified using the interactive response technology system by age group (6 years to less than 12 years and 12 years to less than 18 years, at Visit V2 [Allocation Visit]) so that at least 25% of the subjects are in the younger age group, and by underlying pain condition (cancer/non-cancer-related pain).

Confidential

Protocol KF5503-66
including Amendment 05Page 56 of 137
DMS version 9.0
27 Jul 2017

The following aspects will be requested by the interactive response technology system: body weight, age group of the subject, underlying pain condition, previous opioid treatment for first IMP supply, and preferred strength (25 mg or a combination of 25 mg and 100 mg), if applicable.

10.3.2 Part 2

At Visit VE, subjects will be discontinued from treatment in the interactive response technology system or be offered further treatment with tapentadol PR. Subjects who were treated with morphine PR will be offered further treatment with tapentadol PR in the interactive response technology system.

The following aspects will be reflected by the system: body weight, previous treatment in Part 1 (morphine PR or tapentadol PR) for first IMP supply in Part 2, and preferred strength (25 mg or a combination of 25 mg and 100 mg), if applicable.

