15.1.2.1 Analyses of adverse events

The following overview tables of TEAEs will be generated as described in Section [8.1](#) for Part 1 and the Tapentadol Period of Part 2. For Part 1, in addition to the presentation by treatment arm, descriptive summaries will also be presented overall.

1. Summary of the number and percentage of subjects with at least one:

- TEAE.
- Serious TEAE.
- Non-serious TEAE.
- Unexpected TEAE.
- Related TEAE.
- Related serious TEAE.
- TEAE leading to discontinuation from IMP.
- TEAE leading to discontinuation from the trial.
- Deaths.

For Part 1 in addition:

- TEAE of Part 1, that are ongoing during the Tapentadol Period of Part 2.
- TEAE of Part 1, that are ongoing during the Observation Period of Part 2.
- TEAE of Part 1, that actually started during the Observation Period of Part 2 (within the therapeutic reach of the last IMP intake of the Treatment Period).

For Tapentadol Period of Part 2 in addition:

- TEAE of Part 1, that are ongoing during the Tapentadol Period of Part 2
- TEAE of Tapentadol Period of Part 2, that actually started during the Observation Period of Part 2 (within the therapeutic reach of the last IMP intake of the Tapentadol Period)
- TEAE of Tapentadol Period of Part 2, that are ongoing during the Observation Period of Part 2

2. Summary presenting the number of TEAEs per subject categorized as 0, 1, 2, 3, 4, 5, and >5.
3. Summary of the number and percentage of TEAEs for:
 - TEAEs.
 - Serious TEAEs.
 - Non-serious TEAEs.
 - Unexpected TEAE.
 - Related TEAEs.
 - Related serious TEAEs.
 - TEAE leading to discontinuation from IMP.
 - TEAE leading to discontinuation from the trial.

For Part 1 in addition:

- TEAE of Part 1, that are ongoing during the Tapentadol Period of Part 2.
- TEAE of Part 1, that are ongoing during the Observation Period of Part 2.
- TEAE of Part 1, that actually started during the Observation Period of Part 2.

For Tapentadol Period of Part 2 in addition:

- TEAE of Part 1, that are ongoing during the Tapentadol Period of Part 2.

- TEAE of Tapentadol Period of Part 2, that actually started during the Observation Period of Part 2.
- TEAE of Tapentadol Period of Part 2, that are ongoing during the Observation Period of Part 2.

The percentage denominator will be the total number of TEAEs.

In addition, these overview tables will be presented for subgroups as specified in [Table 4](#).

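### Part 1 adverse-event windows are longer for completers who do not continue on tapentadol than for those who do, so the arms are compared over unequal windows if continuation differs by arm

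*SAP*

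**What the plan says.** SAP 8.2.2 gives two ends for the Part 1 on-treatment period, and SAP 15.1.2 uses that period to assign TEAEs to Part 1.

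- **Continuing in the Tapentadol Period.** The usual case is "If the last administration of IMP during Part 1 is less than 3 days before Visit VE: Visit VE (included". The exception, "If the last administration of IMP during Part 1 is more than 3 days before Visit VE", ends the window 72 hours after that last dose. The Part 2 window opens at the same visit: "Start: Visit VE (excluded in case VE is included in the on-treatment period of Part 1".
- **Not continuing.** "End: Last administration of IMP during Part 1 + 72 hours (included". The current table shows no label for this branch, which may be only a layout matter. The change table in SAP 17.2 identifies it as the children who do not continue. The overview tables in 15.1.2.1 agree, with a row for "TEAE of Part 1, that actually started during the Observation Period of Part 2 (within the therapeutic reach of the last IMP intake".
- **Length of the tail.** For both drugs "the therapeutic reach is defined as 72 hours after (last) IMP intake".

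On presentation, SAP 8.1 states "For Part 1, all presentations will be done per treatment arm, i.e., comparing the tapentadol arm to the morphine arm". Tolerability by arm is a main secondary endpoint (SAP 15.1). Part 1 incidence is crude, affected subjects over subjects in the arm (15.1.2.2). Exposure-adjusted rates are planned for the Tapentadol Period only (15.1.2.3). Safety data are not tested between arms (SAP 15).

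On what follows Part 1, morphine PR is supplied in Part 1 only (Protocol synopsis, Trial treatments), and "Subjects who were treated with morphine PR will be offered further treatment with tapentadol PR" (Protocol 10.3.2). Completers who do not want tapentadol go to the Observation Period (Protocol 8).

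**The concern.** Two children on the same drug, with the same last dose and the same Visit VE, can have different Part 1 windows only because one goes on and the other does not. That decision comes after randomisation, with treatment known. It also differs in kind by arm. A tapentadol child continues on the current drug. A morphine child must change drug, starting tapentadol at 70% of the equivalent morphine dose, and Protocol 11.1.2.1 anticipates withdrawal symptoms there. Different continuation rates are therefore plausible.

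The extra time is also not ordinary time. It is the first days after the opioid stops, when withdrawal-type events would be expected. For a morphine child who stops, these days count in Part 1. For a morphine child who switches, the part of the same 72 hours that falls after VE counts in the Tapentadol Period.

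At stake is the Part 1 tolerability comparison. The overview tables separate Part 1 TEAEs that began in the Observation Period. The tables by preferred term (PT) and by system organ class and preferred term (SOC/PT), where withdrawal-type terms would show, do not.

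**Working it through.** The plan states no figure that depends on this definition, so there is none to reproduce.

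**1. Inputs.** From SAP 8.2.2: VE for completers on Day 14 to 16, last Part 1 dose no earlier than the evening of Day 13, and the two end rules above. From Protocol 14.1: 69 children at 2:1, so 69 × 2/3 = 46 and 69 × 1/3 = 23. Assumed: doses at 08:00 and 20:00, VE at noon. Continuation rates and event rates are also assumed, because the documents give none.

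**2. Extra window for a completer who does not continue.** Extra = (last dose + 3 days) − (VE cut-off). Time runs from 00:00 on Day 1, so the end of Day 15 is 15.00. VE can be taken as the end of the visit day or as noon.

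| Last dose | VE | Last dose + 72 h | Extra, from end of VE day | Extra, from noon at VE |
|---|---|---|---|---|
| Day 15, 08:00 | Day 15 | 17.33 | 2.33 | 2.83 |
| Day 14, 20:00 | Day 15 | 16.83 | 1.83 | 2.33 |
| Day 15, 08:00 | Day 16 | 17.33 | 1.33 | 1.83 |
| Day 13, 20:00 | Day 16 | 15.83 | −0.17 | 0.33 |

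The first two rows are the usual patterns (morning dose on the day of VE, or evening dose the day before): about 1.8 to 2.8 days. Counted from the end of the VE day, that is 2.33/15 = 15.6% and 1.83/15 = 12.2% of a 15-day window. Over all permitted patterns the extra is about 0 to 2.8 days.

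**3. Between-arm effect at a constant event rate.** Let e_T and e_M be the shares continuing.

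- Difference in mean window = (e_T − e_M) × extra. Equal shares give 0. With the extra rounded to 2 to 3 days, 50% against 30% gives 0.4 to 0.6 days, and 60% against 20% gives 0.8 to 1.2 days.
- Shift in incidence = (e_T − e_M) × [F(15 + extra) − F(15)], with F(t) = 1 − exp(−ht). For 50% incidence by Day 15, h = ln 2/15 = 0.0462. With extra = 2.5, F rises by 0.5 × (1 − exp(−0.1155)) = 0.0545. The shift is 0.2 × 0.0545 = 1.1 points, or 0.4 × 0.0545 = 2.2 points.
- Over 30% to 70% incidence and 2 to 3 extra days, the shift is about 0.7 to 1.3 points (50% against 30%) and 1.3 to 2.6 points (60% against 20%).

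**4. If events cluster after stopping.** Suppose 50% of non-continuers are still event-free and a fraction q of these has a first event in the added days. The shift is (e_T − e_M) × 0.5 × q. For q of 10% to 40% it is 1 to 4 points (50% against 30%) or 2 to 8 points (60% against 20%).

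For a single withdrawal-type term in 20% of children who stop, always in the added days and otherwise absent from Part 1, arm incidence is the non-continuing share × 0.20. Continuation of 60% against 20% gives 0.40 × 0.20 = 8% against 0.80 × 0.20 = 16% for two equally tolerated drugs.

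**5. Scale.** One morphine child is 1/23 = 4.3 points and two are 8.7%. Two morphine children with a term therefore pass the 5% threshold for the PT table.

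**The case against.** The strongest reply is that the rule is identical in both arms and attributes periods sensibly. After VE a continuing child takes Part 2 tapentadol, so adding 72 hours to Part 1 would charge events on tapentadol to the morphine arm. A tail has a clear meaning only where dosing stops. This stands, and it is why the 72-hour reach should not simply be extended to everyone.

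Second, the effect at a constant event rate is smaller than one morphine child, and nothing is tested. Both are true. But these tables are the tolerability comparison, no later model adjusts them, and individual terms can move more.

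Third, much is already planned. The overview rows show Part 1 events that began in the Observation Period. Tapentadol Period tables are split by Part 1 treatment (SAP 8.1). Time to onset is summarised by SOC and PT, and AEs starting on the day of VE are listed. The withdrawal scale (SOWS) is completed daily after the last dose. These help but do not give PT or SOC/PT counts over a common window, and at VE the withdrawal scale goes only to children entering the Observation Period.

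Fourth, early stoppers also get the 72-hour tail, but after a shorter treatment time. They can offset or reverse a difference in mean window, so the net direction cannot be predicted.

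**Conclusion.** The point holds as a path-dependent window, not as a demonstrated bias. Part 1 completers are followed for TEAEs to VE or to last dose plus 72 hours according to a post-randomisation choice, and the crude Part 1 PT and SOC/PT tables do not separate the two. A between-arm effect arises if continuation differs by arm. Under the assumed rates it is about 1 to 3 points for any TEAE at a constant rate, and more where events cluster after stopping. It is worth correcting because the remedy is cheap. The primary endpoint and the modified constipation scale in Part 1 are unaffected.

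A reader might infer that the plan builds in a disadvantage for morphine. The documents do not support that: the rule is the same for both arms, no continuation rates are stated, equal rates give no gap, and the direction reverses if fewer tapentadol children continue. A reader might also take the difference as a flat 3 days. Because the last dose may precede VE, it is usually 1.8 to 2.8 days and can be near zero. Nor are events lost: those after VE in continuing children are reported under the Tapentadol Period.

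**What to change.** Keep the 72-hour reach in the TEAE definition and the tables already planned. In SAP 8.2.2 and 15.1.2, add:

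- The Part 1 between-arm TEAE tables (overview, PT, SOC/PT) also with one cut-off for every child: the earlier of Visit VE and last Part 1 dose plus 72 hours. Children with the same dose and visit dates then have the same window whichever path they take. It also covers a gap of exactly 3 days, which neither continuing case covers now.
- One table of AEs starting after VE and within 72 hours of the last Part 1 dose, by arm and by path (Tapentadol Period or Observation Period), including switchers' events now shown only under the Tapentadol Period.
- An explicit label for the non-continuing branch, if it is missing from the source.

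The cost is SAP wording and a few extra tables from dates already collected. Counts in the common-window version will be slightly lower. They will also omit events after VE in early stoppers, which is why this version should sit beside the existing tables and not replace them. In reading the added table, note that the next scheduled contact differs by path: Visit F7D for the Observation Period, M1 for morphine switchers, TP1 for tapentadol continuers.
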